Title: Combined effects of rTMS and botulinum toxin in benign essential blepharospasm: A novel approach
NCT02370875

Protocol Version: 1/5/15

BACKGROUND:

Benign essential blepharospasm (BEB) is a focal dystonia characterized by excessive involuntary closure of the eyelids. BEB is a functionally disabling disorder with significant impact on the quality of life. Due to repeated involuntary closure of eyes, in severe cases, patients become functionally blind despite a normal visual acuity. Chemodenervation with botulinum neurotoxin (BoNT) injections administered every 12 weeks has emerged as an effective first-line therapy for the treatment of BEB. However, the treatment is purely symptomatic and does not modify the disease pathophysiology. Importantly, the clinical benefits are temporary with most patients reporting benefits lasting only about 8-10 weeks. We conducted a retrospective analysis of BEB patients at our movement disorders center that has followed over 250 patients (manuscript submitted) and found that the average duration of benefits from BoNT injections was about 9.5 weeks which is consistent with other studies. Thus BoNT therapy although a first-line therapy for BEB shows suboptimal benefits in many patients. Therefore, there is a clear merit in exploring other options that can potentiate and possibly prolong the effects of BoNT injections.

rTMS refers to application of repetitious transcranial magnetic stimulation (TMS) pulses to a specific brain target at predefined stimulation parameters. We propose a **novel approach** of combining rTMS therapy with BoNT injections in BEB. The **primary goal** of this study is to compare the standard treatment with BoNT versus BoNT combined with a two week course of rTMS therapy. The **central hypothesis** is that rTMS therapy potentiates and prolongs the effects of BoNT therapy in BEB. rTMS therapy has shown beneficial results in many neurological and psychiatric conditions.^{6,7} rTMS therapy is noninvasive and is FDA approved for treatment of medication refractory depression when delivered to the prefrontal cortex.⁸ In our study we will select the anterior cingulate cortex (ACC) as the target of stimulation. ACC has been proposed by many studies as the main sites of pathology in BEB. Anatomically in monkey studies, the ACC has been shown to have clear projections to the upper facial muscles.⁹ In BEB patients, PET study has shown there is an increased glucose uptake in the ACC.^{10,11} fMRI study has also shown an increased brain activity in the rostral ACC in relation to the eye-closure.^{12, 13} Kranz et al in collaboration with [name] lab tested the effects of rTMS of the ACC in BEB. So far to date this is the only rTMS study that is available for review in literature. These investigators found that a single session of low frequency rTMS delivered to the ACC had positive clinical benefits though lasting only for about one hour.¹⁴

The fundamental mechanism of action for rTMS is modulation of brain excitability. 15 rTMS at frequencies of 5-Hz and higher has been found to transiently enhance the excitability, 16 whereas rTMS at frequencies of 1-Hz and lower has been found to depress the cortical excitability. 17 Many rTMS studies have also shown that repeated sessions of rTMS therapy results in cumulative persistent benefits that can last several weeks. For example, in a recent double blind randomized controlled study, low frequency rTMS delivered over eight weeks to Parkinson's disease patients showed positive clinical benefits that lasted 12 weeks beyond the last rTMS session. 18 In this proposal we plan to employ a two week course of rTMS therapy to achieve sustained benefits. With standard BoNT treatment, the peak-dose benefits are seen at about 4-6 weeks after the administration of injections. We plan to introduce rTMS during this peak-dose period (about 6 weeks after BoNT or T1). We will examine the effects of combined therapy at about 10 weeks after BoNT injections (T2) and at about 12 weeks after BoNT injections (T3). We will also measure the physiological effects at these time points. We will use the blink reflex recovery (BRR) curve that reflects the brain stem excitability. An increased BRR indicates that there is increased excitability of facial motor neurons and bulbar interneurons. BRR has been shown to be increased in a significant proportion of patients with BEB. 19,20 According to the animal model of blepharospasm, one of the underlying mechanisms for increased BRR is that a loss of dopamine-containing neurons in the substantia nigra pars compacta causes a decreased inhibition in the blink circuit.²¹

In summary, BEB is a functionally disabling focal dystonia. BoNT therapy is suboptimal in many BEB patients. rTMS therapy is a promising noninvasive therapy and has shown positive benefits in BEB. rTMS therapy can be Protocol Version 08/10/2015

easily combined with BoNT injections to enhance the effects of BoNT in BEB. We plan to collect pilot data on this novel approach in this one year application. The specific aims for the proposal are:

[figure not shown]
Aim 1: Clinical impact of rTMS therapy in BEB.

[figure not shown]
We will determine the clinical effects of 0.2 Hz rTMS therapy of the ACC when combined with BoNT injections in BEB. Comparisons will be drawn between the T1, T2 (about 10 weeks after BoNT) and T3 (about 12 weeks after BoNT) assessments in the clinical scoring of BEB symptoms and patient rating of quality of life. We hypothesize that in comparison to T1 assessment; there will be an increased control of BEB symptoms and patient rating of quality of life at T2 follow-up. These benefits will remain sustained at T3 follow-up though to a lesser extent.

Aim 2: Physiological impact of rTMS therapy in BEB

Aim 2a: We will determine the physiological effects of 0.2 Hz rTMS therapy of the ACC when combined with BoNT injections in BEB. We will record the time course of effects on BRR at T1, T2 and T3 assessments. We hypothesize that in comparison to T1 assessment, BRR will be reduced and reach physiological levels at T2 follow-up. BRR will continue to remain at physiological levels at T3 follow-up though to a lesser extent than at T2.

Aim 2b: We will determine if the effects of 0.2 Hz rTMS therapy on BRR will correlate with clinical scoring of BEB symptoms. We hypothesize that the change in BRR at T2 and T3 will show positive correlation with the improvement in BEB symptoms at these time points.

rTMS will be delivered over the ACC with a figure-of-eight coil.

Figure 1:
A shows the schedule for rTMS intervention and monitoring of clinical and physiological outcomes
B shows the target in the brain for rTMS intervention

METHODS

Study design: We propose a blinded control study of real and sham rTMS with a goal of enrolling about eight subjects (age range 21–80 years) in each treatment arm and ten healthy control subjects for normative physiological data (total 26 16). Subjects diagnosed with blepharospasm or cranio-cervical dystonia who receive BoNT therapy at our center will be approached. The BoNT clinic at our center follows more than 250 subjects with dystonia. Subjects followed at our center regularly fill out a self-reported form to document if they have responded to BoNT and the duration of benefits perceived with BoNT therapy. We will enroll only those subjects who report experiencing positive benefits with BoNT but lasting about 10 weeks or less. We will exclude subjects if they report 1) pregnancy; 2) active seizure disorder; 3) significant cognitive impairment; 4) exposure to neuroleptics; and 5) presence of a metallic body such as pacemaker, implants, prosthesis, artificial limb or joint, shunt, metal rods and hearing aid. We will enroll about 10 healthy age and sex-matched subjects controls for normative electrophysiological data. Controls will be recruited through fliers placed across the campus. All controls will be examined by [name] to ensure that they are neurologically healthy.

We will invite all eligible subjects to an introductory session. During this session the procedures outlined for the study will be explained in detail. We will then obtain an IRB approved informed consent. We will perform medical history and neurological examination using the NINDS Common Data Elements. Each subject will be randomized to receive either real or sham stimulation. We will record the demographics and severity of BEB using the blepharospasm severity scale.²² The BEB subjects followed at our center are scheduled for BoNT treatment about every 12 weeks as per the standard of care. We will start rTMS therapy at about 6 weeks after they have received the BoNT injections. We have chosen this timeframe to coincide the rTMS therapy with the peak-dose effects of the BoNT injections. We will do our best to make sure that the patients are accompanied to the laboratory facility by a friend, relative, or spouse, or we will arrange transportation. Although the physician administering TMS will be aware of the status of the subject in terms of real TMS versus sham-TMS, this physician will play no role in any of the outcome measures, and will not be present during any of the outcome measure assessments. Similarly, the investigators who perform the outcome measures will not be present during any of the TMS sessions, and therefore will remain blinded to the status of the patients with respect to real-TMS versus sham-TMS.

Outcome measures: The primary clinical outcome will be the percentage change in physician rating of BEB symptoms. We will record 5 minute videos of eye blinks for the eye blink rate, number of sustained blinks, and time of eye closure. These videos will be scored by a blinded rater. We will then use the Jankovic rating scale and blepharospasm disability index to rate the improvements. We have IRB approved consent to obtain videos of most patients presenting to our center but the ICF will include a video consent section. The secondary outcome for the study will include the subjective rating by the patients. We will record blink reflex recovery (BRR) as the physiological outcome of rTMS. We will determine the time course effects of rTMS on physiological outcome. We will also determine if the physiological effects correlate with the clinical outcome measures.

Clinical measures:

Physician rating: We will score the eye blink rate, number of sustained blinks, and time of eye closure. An eye blink will be defined as any visible, bilateral, and synchronous contraction of the orbicularis oculi (OO muscle), causing eyelid drop. Blink rate will be expressed as blinks per minute. Sustained spasms of the OO muscle will not be considered blinks and will be counted separately. The time (seconds) of eye closure whenever blinks cause prolonged eye closure (eyes shut > 2 seconds) will be recorded with a stopwatch.¹⁴

Patient rating: We will administer the Craniocervical Dystonia Questionnaire Description for quality of life assessment. The Craniocervical Dystonia Questionnaire (CDQ-24) is a patient-rated health related quality of life (HR-QoL) measure for craniocervical dystonia. It was developed based on issues that are relevant to patients with BEB. It has been validated for use in clinical research. The CDQ-24 measures the impact of Craniocervical

Dystonia on 5 HR-QoL domains. It is composed of 24 items, forming 5 subscales: stigma, emotional well-being, pain, activities of daily living, and social/ family life. Items are rated on a 5-point scale.²³ Each item consists of five statements representing increasing severity of impairment, scored from 0 to 4. Subjects will be instructed to indicate how they have felt during the past two weeks because of dystonia by selecting one of the five statements for each item. Subjects will also rate their symptoms before and after stimulation using a 7-point nominal scale: 1) excellent, 2) very good, 3) good, 4) average, 5) slightly worse than usual, 6) bad or 7) very bad.

Physiological Measure:

Blink reflex recover: We will record surface EMG recordings for both eyes separately from the orbicularis oculi (OO) muscle using Ag-AgCl surface electrodes. The EMG signals will be amplified using D360 amplifiers (Digitimer, Welwyn, UK), band pass filtered (5-2,500 Hz), analog-to-digital-converted using a 1401 AD converter (CED, Cambridge, UK) at a sample rate of 5,000 Hz, and will be collected on a computer. Electrical stimulation will be applied to the supraorbital nerve in the supraorbital notch with a bipolar stimulating electrode and a constant current generator (Digitimer). Single and paired electrical stimuli (conditioning and test) will be delivered and EMG amplitudes will be recorded from the OO muscle. All stimuli will be 0.2 msec in duration and stimulus intensity will be set at 3 times the R2 threshold (lowest intensity that gives an R2 response in at least 5 out of 10 trials). Subjects will be studied at rest, with eyes gently closed. The blink reflex in response to paired stimulation will be assessed at multiple inter stimulus intervals of about 200 msec (6 trials of test and paired stimulus each, pseudo randomized.). Pairs of stimuli will be separated by varying time intervals of 20–40 seconds to minimize habituation. Trials with excessive EMG artifact will be rejected online. Data will be analyzed offline using Signal software (Cambridge Electronic Design, UK). The raw blink recordings will be DC-corrected, rectified, and averaged. The onset latency and duration of R1 and R2 responses will be determined by manual cursor marking of the beginning and end of responses. Peak amplitude of R2 will be calculated within a window from 30 to 60 msec to avoid stimulation artifacts. We will obtain R2 recovery values by dividing the size of R2test [R2T] by the size of conditioning response [R2C]. 19

rTMS therapy:

Real stimulation: rTMS will be delivered over each anterior cingulate cortex, using a figure-of-eight coil connected to a Magstim machine (Magstim Company, Dyfed, UK). We will apply rTMS with 0.2 Hz frequency to the ACC. We will deliver 180 stimuli (around 15 min) with a stimulator output of 100% active motor threshold (AMT). AMT will be assessed at the tibialis anterior muscle with the figure-of-eight coil. The AMT will be defined as the lowest stimulation intensity required to evoke a 150 μV potential in the target muscle. To determine the stimulation site for ACC, the figure-of-eight/double cone coil will be placed over Fz and then moved over the midline of the brain in 0.5-cm steps anteriorly, until the point of maximum motor evoked potential in the orbicularis oculi (OO) muscle (with a latency of 6–8 msec) is reached (about 3.5 cm medial and 5.5 cm anterior to motor cortex). The coil position will be marked on the skin. Constant coil position will be continuously monitored during the experiment. These rTMS sessions will be repeated on a daily basis over 10 days. During rTMS, all patients will wear ear plugs in order to protect the ears from the acoustic artefact associated with the discharge of the stimulation coil.

Sham Stimulation: During sham rTMS, subjects will undergo the same procedure for identifying stimulus location as used in patients receiving real rTMS. Sham rTMS will be administered using the same Magstim coil as used in real stimulation. This coil will be placed on the patient's head in an identical manner however will not be connected to the Magstim device. Instead another coil will be connected to provide stimulation sound. In each stimulation condition, the Magstim will be placed behind the patient and not visible to him or her. Placebo sham coil which produces discharge noise and vibration similar to a real coil without stimulating the cerebral cortex. During rTMS, all patients will continue to wear ear plugs as instructed during the real stimulation sessions.

Safety of rTMS: Repetitive TMS can have undesired side effects. Guidelines for the safe use of rTMS were formulated at the 1st International Workshop on the Safety of TMS.²⁴ These were adopted by the International Federation for Clinical Neurophysiology and subsequently updated.²⁵ The proposed study will use TMS parameters well within the published safety guidelines. We will conduct careful monitoring of the participants and follow all recommended precautions for the application of TMS. Subjects will have a urine pregnancy test done on the first day of the scheduled rTMS visit before rTMS is done.

There will be a potential for direct benefit if the study stimulation helps subject's blepharospasm symptoms. Risks include a neck ache or headache. The study procedure may also cause the nearby scalp muscles to twitch. Although TMS has been used for over 20 years, there is a possibility of unknown risks due to TMS.

Data Safety Monitoring Plan

The principal investigator monitors the patient safety and data collection of each study visit. If she feels there is possible harm to subject safety or the possibility of, any harm due to something new that was learned during the study, she will convene a multi-disciplinary committee of at least 2 health professionals to perform a thorough review of the study details.

Patient Stipends

Payments for mileage reimbursement will be paid to study subjects with blepharospasm. If a hotel visit is required, the study team will make the hotel arrangements for the subjects and the cost will be pre-paid.

Control subjects will be paid a flat rate of \$20 or can be paid for mileage, whichever is greater. If you are paid more than \$75, we will need to collect your social security number.

SAMPLE SIZE, EXPECTED OUTCOME AND STATISTICAL ANALYSIS: With an expected difference of 30% in the primary outcome measure¹⁴ between before (T0) and after rTMS therapy (T1), a standard deviation of 20%, type I error of 5% and power of 80%, the necessary sample size for each group has been determined. In this one year pilot study we propose to enroll a total of 16 BEB subjects with eight subjects in each treatment arm and 16 healthy controls for normative physiological data. Descriptive statistics will be used for the demographic data. Data will be presented as mean (SD) unless otherwise indicated. We will examine each of the dependent measure separately. These include the eye blink rate, number of sustained blinks, the time of eye closure, patient rating of blepharospasm and the BRR cycle. For Aim 1 and Aim2a, each dependent measure will be examined using the following statistical approach. We will conduct a mixed model analysis using time and stimulation arm as repeated factors adjusted for baseline values, and subjects as the random factor. The model will include 2 within-subject factors: treatment (2 levels: active vs sham) and time (3 levels: T1, T1, and T3). If the interaction effects between stimulation arm and time are found as non-significant, they will be dropped. In case of significant main effects, post hoc pairwise comparisons will be corrected using Fisher least significant difference procedure in accordance with the closed test principle; i.e., post hoc comparisons will be declared non-significant if the global p value of the main effect (testing equality of all 2 stimulation arms simultaneously) are non-significant, but will be carried out without further correction in case of a significant global main effect. SPSS version 15.0 for Windows will be used for statistical computations. The 2-tailed significance level will be set at 0.05. For Aim 2b, we will use Spearman correlation test to determine the relation between the change in BRR and change in clinical scores at T2 compared to T1 and at T3 compared to T1.

POTENTIAL PROBLEMS

- 1. Subjects may not meet the criteria, may not tolerate the rTMS therapy or drop out of the study. We will factor in these considerations during recruitment. We propose a sample size of eight subjects in each treatment arm (total 16). We have an IRB approved database of patients followed at our center. In order to meet our target sample, while conducting the retrospective analysis we preemptively identified the BEB subjects that receive suboptimal benefits (36 subjects).
- 2. Quality assurance (QA) on the Magstim machine will be constantly monitored.
- 3. Quality of EMG recordings: The EMG recordings (Delsys, Inc., Boston, Massachusetts) are reliable with high signal-to-noise ratio. We will reduce the noise of the EMG signals by cleaning and lightly abrading the skin.

The University of Florida nor the Principal Investigator hold a patent or license for any material, object or process used in this study. There is no license pending or under consideration or is there any intention to file a patent application at a later date.

Computer-based files will only be made available to personnel involved in the study through the use of access privileges, passwords and encryption. Passwords and encryption are used to ensure that the electronic data is secure and housed in a locked room.

References

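### Aim 1 is stated as improvement from T1, the BoNT peak, with no sham reference, and the analysis section names no real-minus-sham contrast at T2 or T3 to replace it

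*Combined protocol and SAP*

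**What the plan says.** All references are to the combined protocol and SAP.

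- **Aim 1** expects that "in comparison to T1 assessment; there will be an increased control of BEB symptoms and patient rating of quality of life at T2 follow-up", with the gain partly kept at T3. **Aim 2a** expects that "in comparison to T1 assessment, BRR will be reduced and reach physiological levels at T2 follow-up". Neither hypothesis mentions the sham arm.
- **Background, timing.** With standard treatment "the peak-dose benefits are seen at about 4-6 weeks after the administration of injections". rTMS starts in that window, at about week 6, which is labelled T1. T2 and T3 are at about weeks 10 and 12 after injection.
- **Background, duration.** At this centre "the average duration of benefits from BoNT injections was about 9.5 weeks".
- **Methods, Study design.** Patients are randomised to real or sham rTMS. They are eligible only if they report "experiencing positive benefits with BoNT but lasting about 10 weeks or less".
- **Background, goal.** The main comparison is BoNT alone against BoNT plus rTMS. The central hypothesis is that rTMS both strengthens and extends the BoNT effect.
- **Sample size and statistical analysis.** The 30% effect is the difference "between before (T0) and after rTMS therapy (T1"), with SD 20%, two-sided 5% and 80% power, and eight patients per arm. Aims 1 and 2a use a baseline-adjusted mixed model with arm and time. The list of time levels prints T1 twice and omits T2. A non-significant arm-by-time interaction is removed. Post hoc comparisons depend on a significant global main effect, described as a test of equality of the two arms.

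**The concern.** The reference visit is where BoNT works best, and the follow-up visits are where, by the plan's own figures and by selection, it is wearing off. A change from T1 in the real arm is therefore the rTMS effect minus the BoNT benefit lost over the same weeks. Extending BoNT, which is half of the central hypothesis, means holding the T1 level while sham patients decline. Under Aim 1 as written, that success would count as failure.

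The randomised sham arm removes the problem only if the test of each aim is the difference between arms in change from T1. The plan has the data for that test but does not state it. What is at stake is which result will be read as support for the aims.

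**Working it through.** **1. The plan's sample size.** Inputs from the sample-size paragraph: difference 30, SD 20, two-sided alpha 0.05, power 80%, 8 per arm. SD 20 is taken as the SD of the change score, which the plan does not say.

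- Two-sample normal formula: n = 2 × [20 × (1.960 + 0.842) / 30]² = 6.98, so 7 per arm.
- Two-sample t, 8 per arm: noncentrality 30 / (20 × √(2/8)) = 3.0, 14 df, critical value 2.145, power 79.7%.
- Paired t on before-after change: with n = 6, noncentrality 30 / (20/√6) = 3.67, power 83.3%; with n = 8, power 95.1%.

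So 8 is the number that a between-arm comparison needs. A before-after comparison, which is what the sentence describes, would pass 80% with 6.

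**2. What each contrast estimates.** Let R be the rTMS effect and W the BoNT benefit lost from T1 to T2, equal in both arms.

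- Real arm, change from T1: R − W.
- Sham arm, change from T1: −W.
- Real minus sham: R, whatever W is.
- Time effect pooled over two equal arms, which is the time term left if the interaction is dropped: R/2 − W. With R = 30 this is 15 − W.

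With R = W the real arm shows no change and Aim 1 as written fails, although rTMS has kept the whole BoNT benefit.

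**3. Illustration only.** The documents give no value for W, and the plan specifies no paired test. With R = 30, SD of change 20 and 8 patients in the real arm, the chance of a significant improvement from T1 on a paired t-test would be:

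| Assumed W | Expected change | Chance of significant improvement |
|---|---|---|
| 0 | +30 | 95.1% |
| 10 | +20 | 68.1% |
| 20 | +10 | 23.1% |
| 30 | 0 | 2.5% |

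**4. If the 30 is a gross change.** The plan calls it before-after. If sham patients improve by P points (assumed), the between-arm difference is 30 − P. At 8 per arm the noncentrality is (30 − P)/10:

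- P = 0: power 79.7%
- P = 5: noncentrality 2.5, power 64%
- P = 10: noncentrality 2.0, power 46%

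**5. The labels.** In the Background and the aims, T1 is the week-6 visit at which rTMS is introduced. In the sample-size sentence, T0 is before rTMS and T1 is after it. The schedule figure is not shown, so the text alone does not settle which interval the 30% covers.

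**The case against.** The strongest reply is that the aims state expectations while the statistical section states the analysis, and that analysis is controlled: patients are randomised, the stated goal is between arms, the model for Aims 1 and 2a includes arm and baseline, and post hoc testing is gated on equality of the arms. This stands to a large extent. The trial does not lack a control, and a reader should not infer that a within-arm paired test is planned.

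It does not close the gap. No real-minus-sham contrast at T2 or T3 is named as the test of either aim. The time levels are misprinted. The interaction, which carries the difference in change, can be dropped, and the pooled time effect that remains does not isolate rTMS.

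Four stronger readings are tempting and are not supported:

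- **That waning could produce a false positive.** It works against improvement from T1, so it understates benefit.
- **That waning distorts Aim 2a in the same way.** No text says that BRR changes as BoNT wears off. BoNT is described as symptomatic only, and BRR recovery is a ratio of test to conditioning response. Only the missing sham reference carries over.
- **That real minus sham keeps 80% power whatever the waning.** Common waning does cancel, but the figure also needs 30 points to be the between-arm difference, and the plan does not say so.
- **That regression to the mean is built in.** Eligibility rests on duration of benefit, not on a severe score at T1.

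**Conclusion.** The point holds as a flaw in the stated hypotheses and in the named contrast. For Aim 1, the T1-to-T2 change understates an rTMS benefit by the amount of BoNT waning, and pure prolongation would fail the hypothesis. For Aim 2a, the contrast has no sham reference, but a waning bias is not shown. The direction for Aim 1 follows from the plan's own timings. Its size cannot be given, because W is not in the documents.

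The sample size is adequate for a real-minus-sham difference of 30 points with SD of change 20 (79.7%). It is not secured if the 30 is a gross before-after change and sham also improves. The change should be made before the data are analysed, because it decides what the trial can conclude.

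**What to change.** 1. **Aims 1 and 2a:** state each hypothesis as the real-minus-sham difference in change from T1 to T2 (primary) and from T1 to T3 (secondary).
2. **Model:** use T1 as the baseline covariate and T2 and T3 as the outcome visits. Name the between-arm contrast at each visit as the test, and keep the arm-by-time term regardless of its p value.
3. **Labels:** correct the list of time levels, and reconcile T0 and T1 in the sample-size sentence with the Background.
4. **Sample-size sentence:** say that 30 points is assumed to be the real-minus-sham difference and 20 the SD of change. Add that power would be 64% or 46% if sham improved by 5 or 10 points and the 30 were a gross change.
5. **Reporting:** give within-arm changes as description only.

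The cost is rewording two aims, the model paragraph and one sample-size sentence. It needs no new patients, visits or measurements.

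### The plan blinds raters to arm but does not state that visit is masked or scoring order is random, so knowledge of visit could shift the T1-to-T2/T3 contrasts in Aims 1 and 2a, though not the active-versus-sham contrast

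*Combined protocol and SAP*

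**What the plan says.** **Blinding.** The METHODS paragraph before Outcome measures keeps the investigators who perform the outcome measures out of the stimulation sessions; they "therefore will remain blinded to the status of the patients with respect to real-TMS versus sham-TMS". Outcome measures then says of the five-minute recordings: "These videos will be scored by a blinded rater". It does not say what is masked. The document mentions no coded files, concealed visit or date, random scoring order, batch scoring or rater-reliability check.

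**What is rated.** "The primary clinical outcome will be the percentage change in physician rating of BEB symptoms". Under Clinical measures, the rater counts blinks and sustained spasms from video and times prolonged closures with a stopwatch.

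**Blink reflex recovery (BRR).** "Data will be analyzed offline using Signal software". Onset latency and duration of R1 and R2 "will be determined by manual cursor marking of the beginning and end of responses", with no masking stated for this step. "Peak amplitude of R2 will be calculated within a window from 30 to 60 msec", and recovery is the ratio of test to conditioning R2 size. "Trials with excessive EMG artifact will be rejected online".

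**What is compared.** Aim 1: "Comparisons will be drawn between the T1, T2 (about 10 weeks after BoNT) and T3 (about 12 weeks after BoNT) assessments". It predicts better symptom control at T2 than at T1. Aim 2a predicts lower BRR at T2 than at T1. Neither prediction refers to sham. The Background, however, gives the primary goal as a comparison of toxin alone with toxin plus rTMS. The statistical section fits a mixed model with arm, time and their interaction, drops a non-significant interaction, and follows significant main effects with uncorrected pairwise comparisons.

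**The concern.** A within-patient change scored by a person is protected only if that person cannot tell which visit is being scored. The plan conceals arm. It is silent on visit, although stored video makes concealment easy. A rater following the protocol as written could score labelled clips in date order without breaking any rule.

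This matters because the plan can report a time effect as a finding. If the arm-by-time interaction is not significant, which is realistic with eight per arm, it is dropped and a time effect pooled over arms remains. With only two arms, pairwise comparisons among several levels make sense only for time. A change from T1 to T2 would then support Aims 1 and 2a as worded. That estimate absorbs any visit-related shift in scoring. The video measures call for judgement: what counts as a visible contraction, and where a blink becomes a sustained spasm.

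**Working it through.** **1. The plan's own figure.** Inputs from the sample-size section: difference 30, SD 20, two-sided 5%, power 80%, eight per arm.
- Normal formula for two means: n = 2 × (1.960 + 0.842)² × 20² / 30² = 6.98, so 7 per arm.
- Two-sample t test with 8 per arm: noncentrality (30/20) × √(8/2) = 3.0, 14 degrees of freedom, power 79.7%.
- A paired reading would need only 6 patients (power 83%).

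Eight per arm is reproduced by comparing a change score between arms. That supports reading 20 as the SD of the change, although the plan does not say so. It is used that way below, as an assumption.

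**2. Effect of a rater shift on the contrasts.** Assume no true effect, a scoring shift of b points between T1 and a later visit that is the same in both arms, and SD of change 20. The documents give no value for b.
- Pooled time contrast, n = 16: noncentrality b / (20/√16) = b/5, 15 degrees of freedom, critical value 2.131.
- Time contrast within one arm, n = 8: noncentrality b / (20/√8) = b/7.07, 7 degrees of freedom, critical value 2.365.
- Active-versus-sham difference in change: expected value b − b = 0, so noncentrality is 0 for every b.

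| Shift b | Pooled, n = 16 | One arm, n = 8 | Arm difference in change |
|---|---|---|---|
| 0 | 5% | 5% | 5% |
| 5 | 15.5% | 9.4% | 5% |
| 10 | 46.5% | 23.2% | 5% |
| 15 | 80.1% | 44.9% | 5% |
| 20 | 96.2% | 68.1% | 5% |

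A simulation of 40,000 trials per shift, for b from 0 to 20, gave 4.9% to 5.2% for the arm difference. These rates are for one contrast tested alone with a t test, as a simple stand-in for the mixed model. Requiring a significant global test first could only lower them.

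**3. Sensitivity to the SD.** If 20 were instead the SD at a single visit, the SD of change would be 20 × √(2(1 − ρ)), where ρ is the correlation between visits.

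| ρ | SD of change | b = 5, pooled | b = 10, pooled |
|---|---|---|---|
| 0.3 | 23.7 | 12.4% | 35.3% |
| 0.5 | 20.0 | 15.5% | 46.5% |
| 0.7 | 15.5 | 22.7% | 67.5% |

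**4. Is slow drift a plausible source?** T1, T2 and T3 fall at about 6, 10 and 12 weeks after injection, so the gaps from T1 are 4 and 6 weeks. If clips were scored in calendar order with linear drift, a 5-point shift from T1 to T2 would need 5 × 52/4 = 65 points a year, and a 10-point shift 130. Slow drift alone is therefore an unlikely cause of shifts this large. Knowledge of visit is the more credible route.

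**The case against.** **The randomised comparison is not touched.** The primary goal is between treatments, and with arm concealed a shared shift cancels. This stands. A reader might infer that the trial's main comparison is biased; the documents do not support that. The post hoc rule also describes its global test as one of equality of the arms, so how far time contrasts are meant to be reported is unclear. They remain what the aims name.

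**Silence is not a statement.** A reader might infer that raters will know the visit. The plan does not say so: the video rater is simply called blinded and might be masked to visit in practice. All that can be said is that visit masking is not stated.

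**The direction is not known.** It is tempting to say that expectation would produce the predicted improvement. But T1 sits at peak toxin benefit, and patients are enrolled because their benefit lasts about 10 weeks or less. A rater who knows the visit could equally expect worsening at T2 and T3. This stands.

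**BRR is less exposed.** R2 peak amplitude comes from a preset window and recovery is a ratio. Cursors set latency and duration, which are not listed as dependent measures. They reach BRR only if R2 size depends on them, and the plan does not define size. Video scoring has safeguards too: a written blink definition and a 2-second threshold. This stands as a limit on the point.

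**Masking does not rescue the time contrasts.** Even a perfect rater cannot separate rTMS from waning toxin benefit in a pooled change over time. This is correct, and it is why the fix has a second part.

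**Conclusion.** The point holds as a modest, inexpensive improvement. Assessors are blinded to arm, but the plan does not state that visit is masked or that scoring order is random. This leaves the T1-to-T2/T3 contrasts in Aims 1 and 2a open to a rater shift in either direction. With assumed shifts of 5 and 10 points, no true effect and SD of change 20, the false-positive rate is about 16% and 46% pooled and 9% and 23% within one arm. The active-versus-sham contrast stays at 5% provided the shift is the same in both arms. The shift sizes are illustrative and the use of 20 as the SD of change is a reading of the plan; the mechanism depends on neither. The exposure lies mainly in the video scores and is smaller for BRR. The sample size is unaffected.

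**What to change.** 1. **Outcome measures.** State that video clips are coded without date or visit, placed in random order across patients and visits, and scored in one batch after the last T3 visit by a rater masked to both arm and visit.
2. **Physiological Measure (lesser point).** Apply the same coding and random order to offline EMG cursor marking, and say whether R2 size depends on the cursors. Online artifact rejection happens during recording, so this step does not cover it.
3. **Aims 1 and 2a and the statistical section.** Base the conclusions on the active-versus-sham difference in change from T1 to T2 and T3, and report within-arm or pooled time changes as descriptive.

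**Cost.** File coding, a random list and a few sentences of text, with no added visits, procedures or patients. The drawback is that scores are available only at the end; the plan describes no interim analysis that would need them sooner.
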